#### Withdrawal from study

Participants may withdraw their consent for the study at any time, without providing a reason for this. If this occurs, this will be documented on a study completion/ discontinuation form and the patient notes. Although the participant is not required to give a reason for discontinuing their study treatment, a reasonable effort will be made to establish this reason while fully respecting the participants' rights. Any data collected up to the point of the participant's withdrawal will be retained, and used in the final analysis, and this is made clear to the patient at the time of consent. Any samples collected up to the point of the participant's withdrawal will be retained, and used in the final analysis, unless the participant requests otherwise, and this is also made clear to the patient at the time of consent.

Excessive participant withdrawal from follow-up has a negative impact on a study. Centres will explain the importance of remaining on study follow-up to participants, and that changes to planned treatment need not imply withdrawal from the study. Nevertheless, if participants do not wish to remain in the study their decision must be respected. If the participant explicitly states their wish not to contribute further data to the study, this will be recorded on the study completion/discontinuation form and in the patient notes. Withdrawn participants will not be replaced. For those participants who do not want to actively participate in follow up the local study team will continue to collect data from medical notes and other available healthcare sources unless the participant specifically refuses permission for this. Remote follow up e.g., via telephone calls may also be used if the participant does not wish to attend study visits in person.

#### 9.11 Loss to follow-up

Participants will be defined as lost to follow up if they repeatedly fail to return for scheduled visits and are unable to be contacted by the site. Reasonable attempts should be made to contact the participant where possible, before they are considered lost to follow-up. Data from hospital records may still be collected if possible and this is explained in the PIS. If a participant is lost to follow up, this will be recorded in the CRF using the study completion/discontinuation form.

#### 9.12 Ethnicity data

In addition to collecting ethnicity data for EXPERTS-ALS participants, all staff on site delegation logs will be asked to complete an optional question on their ethnicity. The purpose of

collecting this information is to look at the demographics of our trial workforce as this may be a contributing factor in the diversity of participants recruited for the trial. Anonymised data may be aggregated with that from other studies to inform future research. CTRU will send a link to an online questionnaire to all members of staff listed on site delegation logs. The first page of the questionnaire will provide information about the data we are collecting and why. Names and email addresses will not be collected.

## **10. Safety Reporting**

ICH-GCP requires that both investigators and sponsors follow specific procedures when reporting adverse events/reactions in clinical studies. These procedures are described in this section. IMP-specific reporting may be required for some IMPs, in which case the details will be included in the IMP-specific appendices. Additional guidance is provided in a study-specific SOP.

#### **10.1 Definitions**

Term	Definition				
Adverse Event (AE)	Any untoward medical occurrence in a study participant. Refer to Section 10.2 for study-specific exemptions.				
Serious Adverse Event (SAE)	
 
An AE which is serious, defined as any untoward medical occurrence or effect that:
 
Results in death
 
Is life-threatening*
 
Requires hospitalisation or prolongation of existing hospitalisation**
 
Results in persistent or significant disability or incapacity
 
Congenital anomaly/birth defect
 
Other important medical event ***
 
				
Adverse Reaction (AR) or Serious Adverse Reaction (SAR)	Any AE or SAE that is judged, in the opinion of the PI, to be related to an investigational medicinal product.				
Suspected Unexpected Serious Adverse Reaction (SUSAR)	A SAR, the nature or severity of which is not consistent with the reference safety information for the IMP.				

Table	3:	Safety	reporting	definitions
TUNIC	٠.	Juicty	reporting	actinitions

\*The term life-threatening in the definition of a serious event refers to an event in which the patient is at risk of death at the time of the event; it does not refer to an event that hypothetically might cause death if it were more severe, for example, a silent myocardial infarction.

\*\*Hospitalisation is defined as an inpatient admission, regardless of length of stay, even if the hospitalisation is a precautionary measure for continued observation. Hospitalisations for a preexisting condition, that has not worsened or for an elective procedure for a condition which has not worsened do not constitute an SAE.

\*\*\*Other important medical events that may not result in death, be life-threatening, or require hospitalisation may be considered a serious adverse event/experience when, based upon appropriate medical judgement, they may jeopardise the patient and may require medical or surgical intervention to prevent one of the outcomes listed in this definition.

## 10.2 Study specific exemptions

Events that are expected due to the participant's ALS (even if they meet the definition of Serious as defined in section 10.1) should **not** be recorded or reported as adverse events.

Due to the heterogeneity of disease progression in ALS the Principal Investigator, or delegate, is required to assess whether the event is consistent with expected disease progression in the participant. Events consistent with disease progression should be recorded in the participant's medical notes only, with the exception of hospitalisation due to disease progression which should be recorded on the ALS Progression Hospitalisations form and death which should be recorded on the Study completion/discontinuation form in the CRF. The study team will inform the patient's local ALS care team (nurse/consultant) or GP in the event of disease progression occurring so that appropriate management can be initiated.

If the event is related to ALS but judged to be an unexpected worsening of the condition and/or possibly related to participation in the trial/ trial medication it should be treated as an adverse event, recorded in the participant's medical notes and recorded/reported as an AE. The seriousness of the AE should be assessed as per section 10.1 and if it meets the definition of serious then it should be reported as per section 10.5.

Exemptions may include, but are not limited, to:

- Symptoms and signs due to ALS and its expected progression e.g. minor cramps, fasciculations, sialorrhea, mild musculoskeletal discomfort, breathlessness.
- Hospitalisation:
  - for gastrostomy insertion
  - $\circ$  due to falls
  - o due to choking and panic attacks (pharyngeal spasm)
  - o for secretion management
  - o due to aspiration pneumonia
  - o associated with complications of NIV use (including titration of NIV pressure)
  - $\circ \quad$  for weaning of ventilation for end of life care
  - $\circ~$  for end of life care, particularly during the last 24-48hrs of life
  - o due to carer burden
  - o due to inability to manage activities of daily living and lack of social support
- Death
  - o caused by type 2 respiratory failure

Where there are any modifications to AE reporting for individual IMPs, these are detailed in the appendix for that IMP.

## 10.3 Identification and assessment at site

#### Identification

AEs/SAEs which are not exempt (as per Section 10.2) will be recorded in the eCRF from consent until the participant has completed their involvement in the trial, up to week 24.

Participants will be asked about AEs/SAEs at every study visit with open-ended and nonleading verbal questioning. Participants will also be asked if they have been admitted to hospital or had any accidents. AE data may also be identified via information in the medical records.

## Seriousness

AEs must be assessed by the investigator for seriousness in order to determine if the event is an SAE. Assessments must be based on the definitions provided in Section 10.1. The notification procedure for SAEs is detailed in Section 10.5.

#### Causality (relatedness)

The relatedness of all AEs will be assessed by the site Principal Investigator or delegate and recorded on the AE form. The relatedness to the IMP will be categorised as follows:

- Reasonable probability of being related where the nature of the event, the underlying medical condition, concomitant medication or temporal relationship make it possible that the AE has a causal relationship to the study drug.
- No reasonable probability of being related where an event is not considered to be related to the IMP.
- Not assessable where there is insufficient information to assess relatedness.
   Follow up reports for any events categorised as 'not assessable' should be submitted as soon as possible to update the causality assessment when more information is available.

For the purposes of regulatory reporting, if a causality assessment is not provided by the site, or is recorded as not assessable, SAEs will be deemed to be related until the site Principal Investigator or delegate confirms otherwise.

#### Severity (intensity)

The severity of all SUSARs will be assessed by the investigator as follows:

- Mild an event that is easily tolerated by the participant, causing minimal discomfort and not interfering with routine activities.
- Moderate an event that is sufficiently discomforting to interfere with routine activities.
- Severe an event that prevents routine activities.

The worst severity grade for each SUSAR will be recorded in the Prospect database.

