## **10.7 CTRU responsibilities**

CTRU will assess all SARs for expectedness in collaboration with the CI. An unexpected adverse reaction is one which is not previously reported in the Reference Safety Information (RSI) used in the study, or one that is more frequent or more severe than reported in the RSI. If a SAR is assessed as 'unexpected', it is classified as a SUSAR.

The RSI to be used in the study will be section 4.8 of the SmPC for the relevant IMP in the version which has been submitted to and approved by the MHRA for this trial.

The Sponsor has delegated CTRU responsibility for the reporting of SUSARs and other SARs to the regulatory authorities and the research ethics committee as appropriate. CTRU will also keep all investigators informed of any safety issues that arise during the course of the study. CTRU will report all SAEs to the Sponsor as documented in the delegation of duties agreement.

The DMEC and TMG will also receive information on all AEs and SAEs, at a frequency agreed with each committee and documented in the appropriate charter/terms of reference.

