- 1. Superiority to current reference drug: If a candidate drug has demonstrated superiority over the current reference drug, it warrants consideration as a new reference drug. This evaluation should adhere to the predefined criteria established in the protocol.
- 2. Non-inferiority to current reference drug: A candidate drug may also be considered as the new reference drug if it has been shown to be non-inferior to the current reference drug following the criteria established in the protocol. This consideration may be triggered by factors such as improved tolerability or when the DMEC believes that sufficient data have been accumulated for the current reference drug within the context of the platform trial so that a change to a new reference drug is warranted.

Further details of the primary outcome analysis will be pre-specified in the statistical analysis plan. In the event that a candidate drug has a prolonged titration phase to reach the target dose, the statistical analysis plan may be amended to account for this.

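### Severity is graded only for SUSARs, although excess severity is one ground for calling a reaction a SUSAR, and other adverse events need no grade at all

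*Protocol*

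**What the plan says.** Section 10.3 of the protocol sets out what the site assesses for each event. Seriousness and relatedness to the drug are required for adverse events in general. Severity is treated differently: "The severity of all SUSARs will be assessed by the investigator as follows", on a scale of mild, moderate and severe. The data-capture rule has the same scope: "The worst severity grade for each SUSAR will be recorded in the Prospect database".

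The Section 10.1 table defines a SUSAR as "A SAR, the nature or severity of which is not consistent with the reference safety information for the IMP". Section 10.7 gives the procedure. "CTRU will assess all SARs for expectedness in collaboration with the CI", and an unexpected reaction is one absent from the RSI "or one that is more frequent or more severe than reported in the RSI". The section then states: "If a SAR is assessed as 'unexpected', it is classified as a SUSAR".

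Tolerability also matters outside pharmacovigilance. Safety and tolerability form the first secondary objective in Section 3.2. Section 11.1 plans Poisson regression of adverse events and serious adverse events, with comparisons between concurrently randomised arms. It also allows a non-inferior candidate to replace the reference drug, and says of that choice: "This consideration may be triggered by factors such as improved tolerability". The same section lets a lower-ranked drug go forward to Phase III on the strength of a better safety profile.

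**The concern.** There are two separate consequences.

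The first is order. If a reaction is of a known type but worse than the RSI describes, its severity decides whether it is a SUSAR. The protocol asks the investigator, who knows the patient, for a severity grade only once that decision has been made. The central team must therefore decide without a required, standardised grade from the site.

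The second is comparison between arms. The side effects that Appendices 2 to 4 name as common are mostly symptoms that would rarely be serious in the regulatory sense: nausea and diarrhoea for metformin, constipation and oedema for nifedipine, somnolence and headache for ropinirole. For such events, severity is the natural way to separate a nuisance from something that stops a patient functioning. The trial has no placebo arm, so comparison between active arms is its main internal source of comparative safety information. Without a required grade, that comparison cannot be broken down by severity.

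**Working it through.** The protocol gives no figure on this point and no arithmetic applies. The check sets the safety sections side by side.

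**Which assessment is required for which events**

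| Assessment | Events covered | Source |
|---|---|---|
| Seriousness | Adverse events generally | Section 10.3, Seriousness |
| Relatedness | All adverse events | Section 10.3, Causality |
| Expectedness | All SARs | Section 10.7 |
| Severity grade | SUSARs only | Section 10.3, Severity |

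Severity is the only one of the three site assessments that is restricted in this way. Section 10.4 asks for fuller information on SAEs, SARs and SUSARs, but does not name a severity grade.

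**The order of decisions**

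1. The site records an adverse event and assesses seriousness and relatedness.
2. A serious, related event is a SAR.
3. The trials unit, with the chief investigator, compares the SAR with the RSI. Section 10.7 gives three grounds for calling it unexpected: (a) not previously reported in the RSI, (b) more frequent, (c) more severe. Section 10.1 names nature and severity.
4. If any ground is met, the SAR becomes a SUSAR.
5. Only now does Section 10.3 require the investigator's severity grade.

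Grounds (a) and (b) need no severity grade, so steps 3 to 5 work for them. Ground (c) needs severity at step 3, while the grade is first required at step 5. The ordering fault is therefore confined to ground (c).

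**What is available at step 3 without the grade.** Section 10.5 requires an SAE form, completed by the investigator or later checked and signed by the investigator, within 24 hours of site awareness, with follow-up reports until recovery or stabilisation. The trials unit can form a view of severity from that description. The judgement is possible, but rests on no required grade.

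**What is available for comparing arms**

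- Seriousness and relatedness (Section 10.3).
- Dose reduction, interruption or stopping because of a related, clinically significant event (Section 6.7).
- Early discontinuation of treatment, on its own form (Section 9.10).
- Adherence at each visit (Section 6.6).

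A severity grade is absent from this list for every event that is not a SUSAR. Dose reduction is also not comparable across all current arms: Appendices 2 to 5 allow it and Appendix 6 does not.

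**Whether a later document could repair it.** This is a data-collection rule. A statistical analysis plan can define how recorded grades are analysed but cannot create grades that were not recorded, and each arm completed under the present rule adds ungraded events.

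**The case against.** The strongest reply is that expectedness is not judged from a three-level grade at all. It is judged against section 4.8 of the relevant SmPC, from an investigator-signed SAE report and its follow-up. Missing causality is handled conservatively, with the SAE treated as related, and the DMEC and TMG see all adverse events and SAEs. On tolerability, the protocol promises no severity-stratified analysis, the reference-drug rule is discretionary, and the measures listed above are direct evidence of how well a drug is tolerated. The drugs are repurposed, with known side-effect profiles. The scale is anchored on interference with everyday activity, which in ALS also falls because of the disease. Grading and updating every event across about 700 participants and 11 centres is more work than a single tick.

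Much of this stands, and it limits what can be claimed. A reader might infer any of the following, none of which the protocol supports:

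- **That SUSAR classification as a whole is circular.** Only the severity ground is affected, and an informal judgement remains possible there.
- **That SUSARs will be missed.** Nothing shown establishes that an earlier grade would change any classification.
- **That no severity information exists for ordinary events.** The protocol does not require a grade, but the AE and SAE forms, the safety SOP and Figure 4 are not shown and may collect one.
- **That a given percentage of the events used for expectedness lacks a grade.** Expectedness is assessed for SARs only, not for all adverse events, and the protocol gives no counts.
- **That tolerability cannot be compared.** It can, but not by severity grade.

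The reply does not explain why the protocol makes severity part of the SUSAR definition, provides a scale for it, and then asks for the grade only after the definition has been applied. Nor does seriousness replace severity for the mainly non-serious symptoms expected with these drugs.

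**Conclusion.** The point holds within narrow limits. Section 10.3 places the severity grade after the classification it should inform, on one of the three grounds for unexpectedness in Section 10.7. It also leaves all events other than SUSARs without a required grade, so the adverse-event comparisons and the tolerability and safety-profile considerations in Section 11.1 cannot be split by severity.

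The consequence is a weaker basis for one route of safety classification and less informative tolerability evidence, not a failure of either. No numerical size can be given, because the protocol states no expected rates of SARs or adverse events. The conclusion assumes that the protocol text governs what sites must record. If the forms or the safety SOP already ask for severity more widely, the problem becomes an inconsistency between documents, and Section 10.3 still needs correcting. The change is worth making because it is cheap and grades not recorded at the time cannot reliably be recovered later.

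**What to change.** Amend Section 10.3 as follows.

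1. The investigator grades every SAE and SAR on the existing three-level scale and enters the grade on the SAE form, so that it is available before the trials unit assesses expectedness. The grade is updated if follow-up shows a worse course. This is the minimum change.
2. Preferably, the same grade is recorded for every reportable adverse event on the adverse event form, which already carries relatedness. Events exempt under Section 10.2 stay exempt.
3. The sentence on what is stored in the database is widened to match.
4. The forms, the safety SOP and Figure 4 are checked against the amended text. If they already collect severity more widely, Section 10.3 is brought into line with them.

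The cost is one extra field per event, plus the site's time to judge and update it; the minimum change confines this to serious events. The limitation is that a scale based on everyday activity may partly reflect ALS progression, so grades should be read with that in mind when arms are compared. No treatment or clinical rule changes.

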#### **10.4 Recording and reporting**

AEs and ARs will be recorded from the time of consent for trial entry until the participant has completed their involvement in the trial, up to week 24.

AEs and ARs except those exempt as per section 10.2 will be recorded on the adverse event report form, within the study database, including those that fulfil the criteria for being serious (see section 10.1). Sites are asked to enter all available information onto the study database as soon as possible after the site becomes aware of the event.

Out of range lab values will only be recorded as an AE if they are considered clinically significant and require intervention to treat.

SAEs, SARs and SUSARs will require more detailed information to be recorded. In such cases, the event must also be reported to the Sheffield CTRU within 24 hours of the site becoming aware of the event. The CTRU will notify the Sponsor of each of these events in accordance with the Agreement between Sheffield Teaching Hospitals and University of Sheffield.

## **10.5 SAE notification procedure**

Site staff must notify CTRU of all SAEs within 24 hours of becoming aware of the event, with the exception of the events listed in Section 10.2. All SAEs must be reported on the Serious Adverse Event (SAE) reporting form and sent to CTRU by email: [contact] within the reporting timelines.

The SAE form must be completed by the investigator (a clinician named on the delegation log who is responsible for the participant's care). In the absence of the investigator the form will be completed by a member of the study team and emailed as appropriate. The responsible investigator will subsequently check the SAE form, make changes as appropriate, sign and re-send the form to CTRU as soon as possible.

Receipt of the initial report should be confirmed by CTRU within one working day. The site research team should contact the study team at CTRU if confirmation of receipt is not received within one working day.

Concomitant medications are recorded throughout the study and will not be collected on SAE forms as standard. However for any event classified as a SAR or SUSAR CTRU may request additional information on concomitant treatments to facilitate onward reporting.

#### Follow up

Initial SAE reports must be followed by detailed reports when further information becomes available.

SAEs must be followed up until clinical recovery is complete and laboratory results have returned to normal or baseline, or until the event has stabilised. Follow up information will be provided on an SAE form marked as such. This may continue beyond a participant's involvement in the trial and this is specified in the PIS. Follow up of unresolved SAEs (SAEs that have not resolved or stabilised, or where causality and/or expectedness assessments are incomplete) will continue until database lock for the arm to which they were randomised.

Further clarification on the reporting process can be seen in Figure 4.

